#### Per-Protocol (PP) Analysis Set

All subjects included in the ITT analysis set who complete the study as planned with no major protocol deviations will be included in the PP analysis set. Membership in this analysis set will be determined at a data review meeting prior to unblinding the randomization. This analysis set will be used as a sensitivity analysis relative to the ITT analysis set.

### **3.3 Procedures for Handling Missing Data**

The primary analysis will be based on the observed data where average weekly SBMs and CSBMs will be standardized to 7-day frequencies. This amounts to missing days during the week being imputed with the mean for the non-missing days. A valid week will require at least 4 non-missing diary days. Hence, for the primary analysis, weeks with less than 4 diary days are treated as a non-responder for that week. To further assess the impact of missing weeks on the efficacy analyses, a sensitivity analysis will be carried out by treating weeks with less than 4 diary days as a responder for that week.

The valid week rule will also apply for stool consistency and straining score although it is assumed that if the diary was filled out for frequency of stools, it would also be filled out with respect to these items. However, the average weekly stool consistency and the average weekly straining score will be calculated on the observed number of responses without any standardization. For the purposes of calculating an average, days with no stools reported (i.e., a 0 was recorded for the answer to IVRS question) will be scored as 0 for average weekly stool consistency and average weekly straining score.

An endpoint week will be defined as the last valid week during the first 12-weeks of the treatment period and the last valid week of the 26-week treatment period where each weekly

efficacy variable was obtained. This amounts to creating an endpoint last observation carried forward such that each subject's endpoint value represents the last experience while receiving study drug during the first 12-weeks and the total 26-week treatment period. In the few cases where no efficacy data is collected during the 12-week treatment period, the endpoint week will be considered a non-response or missing if no frequency or stool consistency data are obtained.

Otherwise, all other observed data will be used in the analyses.

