5.5. Rescue Medication

The following rescue medications are allowed for severe constipation (ie, at least 72 hours after the subject's previous BM or when symptoms become intolerable):

- Bisacodyl (5 mg tablet or 10 mg suppository)

Rescue medication is allowed during the screening period, provided that there are no more than 2 uses and that none is used during the 2 days before randomization.

Subjects are instructed to contact the investigator prior to taking a rescue medication for severe constipation, and all rescue medication usage and time of usage must be recorded during the subject's daily call to the IVRS. A bowel movement will not be considered a spontaneous bowel movement (SBM) if it is reported less than 24 hours from the use of a rescue medication.

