8.3.2.6 Bowel Movement Frequency

“How many bowel movements have you had in the past 24 hours?”

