8.3.2.6.3 Stool Consistency using BSFS ([Appendix B](#)) (For each bowel movement)

“Refer to the Bristol Stool Form Scale given to you. Please enter the number that best describes the consistency of bowel movement <number> following the scale:

Press 1 for separate hard lumps, like nuts (hard to pass)

Press 2 for sausage shaped but lumpy

Press 3 for like a sausage but with cracks on its surface

Press 4 for like a sausage or a snake, smooth and soft

Press 5 for soft blobs with clear cut edges (passed easily)

Press 6 for fluffy pieces with ragged edges, a mushy stool

Press 7 for watery, no solid pieces (entirely liquid)”

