8.3.2.6.4 Straining (For each bowel movement)

“How much did you strain during the bowel movement? Please use the following scale. Press 1 for not at all. Press 2 for a little bit. Press 3 for a moderate amount. Press 4 for a great deal. Press 5 for an extreme amount.”

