Average weekly SBMs will be calculated as described above for average weekly CSBMs. Change from baseline for each week of the 26-week treatment period will be summarized using the observed data. An endpoint week will be defined as the last valid week during the treatment period with an average weekly SBM.

Subjects will record the consistency of each of their bowel movements on a daily basis through the IVRS utilizing the BSFS scale (Appendix B of the protocol). The average weekly stool consistency will be calculated as the average score for all valid SBMs during the week. For purposes of calculating an average, days with no stools will be scored a 0. Change from baseline for each week of the 26-week treatment period will be summarized using the observed data. Baseline will be calculated as described for the CSBMs and SBMs. An endpoint week will be defined as the last valid week during the treatment period with an average weekly stool consistency.

Straining will be scored for each SBM using the scale 1 = not at all, 2 = a little bit, 3 = a moderate amount, 4 = a great deal, 5 = an extreme amount. The average weekly straining score will be calculated as the average score for all valid SBMs during the week. Change from baseline for each week of the 26-week treatment period will be summarized using the observed data. Baseline will be calculated as described for the CSBMs and SBMs. An endpoint week will be defined as the last valid week during the treatment period with an average weekly straining score.

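### Scoring no-stool days as 0 makes weekly stool consistency and straining follow stool frequency, even when the stools themselves do not change (SAP 3.3)

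*SAP*

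**What the plan says.** Patients rate consistency and straining for each bowel movement. The lowest answer on each scale is 1: for consistency, "Press 1 for separate hard lumps, like nuts (hard to pass" (Protocol 8.3.2.6.3); for straining, "Press 1 for not at all. Press 2 for a little bit" (Protocol 8.3.2.6.4). The scales end at 7 (watery) and 5 (extreme).

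SAP 3.3, like Protocol 10.4, averages the observed responses without standardising to 7 days, and adds that days with no reported stool "will be scored as 0 for average weekly stool consistency and average weekly straining score". The trigger is an answer of 0 to the frequency question, "How many bowel movements have you had in the past 24 hours" (Protocol 8.3.2.6).

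In SAP 2.3.1 the consistency paragraph repeats the rule: "For purposes of calculating an average, days with no stools will be scored a 0". The straining paragraph next to it does not: "The average weekly straining score will be calculated as the average score for all valid SBMs during the week". Protocol 10.7.5 has the same pattern.

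SAP Table 2-1 lists both variables as Secondary and contains no version without the zeros. SAP 3.7.1 analyses change from baseline by ANCOVA and plots both over time. SAP 3.6 calls secondary p-values descriptive.

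**The concern.** A 0 is not a rating that a patient can give. On straining it lies below the best answer, so a valid week without any stool gets the best possible score, while a patient with a stool every day cannot score below 1. On consistency it lies below the hardest stool.

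The number of zeros depends on how often the patient has a stool, and the drug is meant to increase that. More stool days raise mean consistency, which looks favourable, and raise mean straining, which looks unfavourable. A difference between arms in either score therefore cannot be read as a difference in stool form or in straining. For consistency the distortion flatters the arm with more stool days. For straining it hides a true benefit and can reverse its sign.

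**Working it through.** **Inputs.** From the documents: the two scales, the zero rule, averaging over observed responses, and an entry limit of 5 SBMs per week (Protocol 5.4), which leaves on average at least 7 - 5 = 2 SBM-free days per week at screening. The documents give no expected SBM frequency, consistency or straining value, so there is no figure of the plan to reproduce, and every other input below is an assumption.

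**Formulas.** The text leans towards pooling ratings over the week, but because it scores days as 0, averaging by day first is also possible.

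- Pooled: sum of SBM ratings / (SBMs + no-stool days)
- By day: sum of daily mean ratings / (SBM days + no-stool days)

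**One subject** (complete diary, one SBM per SBM day, so both readings agree):

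| | 2 SBM days | 5 SBM days |
|---|---|---|
| Straining 4, then 2 | (2×4)/7 = 1.14 | (5×2)/7 = 1.43 |
| BSFS type 2 throughout | (2×2)/7 = 0.57 | (5×2)/7 = 1.43 |

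Straining falls by half and is recorded as worse. Unchanged stools are recorded as softer.

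**Two arms.** Assume 3.0 SBMs/week on placebo and 4.5 on tenapanor, per-SBM straining 3.1 against 2.6 (a benefit of -0.50), mean form 3 in both arms, and every day without an SBM a no-stool day. Daily SBM counts are Poisson, without or with gamma variation between subjects (CV 0.4). The expected score is then the per-SBM mean times a weight. Pooled weights come from 1,000,000 simulated weeks per setting. By-day weights are 1 - exp(-r/7) and, with gamma, 1 - (1 + 0.16r/7)^-6.25, where r is SBMs per week.

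| Weight | 3.0/week | 4.5/week |
|---|---|---|
| Pooled, Poisson | 0.385 | 0.533 |
| Pooled, gamma | 0.374 | 0.512 |
| By day, Poisson | 0.349 | 0.474 |
| By day, gamma | 0.339 | 0.458 |

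Straining, tenapanor minus placebo:

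- Pooled: 2.6×0.533 - 3.1×0.385 = +0.19; 2.6×0.512 - 3.1×0.374 = +0.17
- By day: 2.6×0.474 - 3.1×0.349 = +0.15; 2.6×0.458 - 3.1×0.339 = +0.14

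Consistency with identical form:

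- Pooled: 3×(0.533 - 0.385) = +0.44; 3×(0.512 - 0.374) = +0.41
- By day, from unrounded weights: +0.38 and +0.35

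**When the straining sign flips.** With placebo at 3.0 and a true benefit of -0.50, the zero-scored difference is +0.04 to +0.07 at 4.0 SBMs/week on tenapanor and -0.06 at 3.5. At equal frequency it is -0.17 to -0.19, which is the benefit compressed. The break-even frequency is 3.71 to 3.78 over all readings; by day with Poisson counts it is -7 ln(1 - 3.1×0.3486/2.6) = 3.76. The gap needed is therefore about 0.7 to 0.8 SBMs/week.

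**Rescue use.** A bowel movement does not count as spontaneous "if it is reported less than 24 hours from the use of a rescue medication". A day with only such a movement adds neither a rating nor a 0. At 3.0 SBMs/week about 4.6 days have no SBM. If 20% of these are such days, that is about 0.9 days/week, close to the screening allowance, "provided that there are no more than 2 uses" in 14 days. With 20% on placebo and none on tenapanor, at 4.5 against 3.0 SBMs/week, straining is -0.01 to +0.03 and consistency +0.21 to +0.29.

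**The case against.** The rule is explicit, pre-specified and shared by protocol and SAP. It keeps nearly every valid week. For consistency, ranking a day without a stool below a hard stool is a defensible composite in a constipation trial. Averaging over SBMs conditions on a post-randomisation outcome. Average weekly SBMs are reported alongside, so a change in frequency is visible. If tenapanor adds stool days, the straining distortion works against the drug and cannot create a false benefit. Keeping the rule and adding an SBM-only sensitivity analysis would be cheaper.

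The point about conditioning stands, and the fix has to allow for it. The composite argument does not carry over to straining, where the 0 sits at the favourable end. Seeing the frequency change does not let a reader separate it from form, and frequency already has its own secondary outcomes. The cheaper option would reveal the problem but leave the main tables and figures under labels that they do not fit.

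A reader might infer that the SAP contradicts itself on straining. It does not: SAP 2.3.1 omits a rule that 3.3 states outright. The texts need aligning, since someone working from 2.3.1 alone would derive a different variable. The separate programming specification (SAP 4) may settle derivation details but is not available here.

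**Conclusion.** The concern holds for two named secondary outcomes. As defined, they combine stool frequency with stool rating and cannot be read as form or straining alone. The mechanism follows from the scales and the rule, provided that some no-stool days remain and their number changes; with a stool every day there are no zeros. The sizes, about +0.35 to +0.44 for unchanged consistency and +0.14 to +0.19 in place of -0.50 for straining, rest on assumed frequencies, ratings and count distributions.

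Two stronger readings are tempting. One is that tenapanor's straining result will come out reversed. The documents give no expected frequency, a reversal of a -0.50 benefit needs a gap of about 0.7 to 0.8 SBMs/week or more, and it can vanish if rescue use differs by arm. The other is that the efficacy conclusion is compromised. The primary and key secondary endpoints use CSBMs and abdominal pain, not these scores, and neither they nor the type I error are touched.

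**What to change.** Change the SAP before unblinding. Protocol 10 provides for such changes in the SAP, without a protocol amendment.

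1. In SAP 3.3 and 2.3.1, define both variables as the mean over all SBMs in a valid week, at baseline and on treatment.
2. Set valid weeks without an SBM to missing for these two variables, and report their number by arm and week.
3. In SAP 3.5, state that for these two variables the endpoint week is the last valid week with a score. SAP 3.5 now fixes it by last dose and at least 4 diary days, so a full diary week without an SBM would be an endpoint without a score, whereas 2.3.1 and 3.3 look for a week with a score. State also that baseline uses the one available screening week when the other has no SBM, and count subjects lacking both by arm.
4. Keep the zero-scored version as a labelled sensitivity analysis that combines frequency and rating. Say whether it pools or averages by day, and how days with only non-spontaneous movements count.

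The work is SAP wording, derivation code and one sensitivity table per variable. The price is some missing weeks and subjects, possibly unequal by arm. Under the same assumed count models, the share of weeks without an SBM is exp(-r) or (1 + 0.16r)^-6.25: 5% to 9% at 3.0 SBMs/week and 1% to 3% at 4.5. At an assumed baseline of 2.0, 25% to 31% of subjects lack an SBM in at least one screening week and 2% to 5% in both. Hence the baseline rule, the counts by arm and the sensitivity analysis.

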5.7. Removal of Subjects from Therapy or Assessment

Subjects will be discontinued from the study if any of the following conditions apply:

1. A subject experiences a study drug related serious adverse event.
2. A subject experiences severe diarrhea defined by a Bristol Stool Form Score ([Appendix B](#)) of ≥ 6 AND stool frequency ≥ 7 /day (Common Terminology Criteria for Adverse Events [CTCAE] v4.0, Grade 3) for 2 consecutive days.

Subjects will be informed that they have the right to withdraw from the study at any time for any reason, without prejudice to their medical care. The Investigator may remove a subject if he/she feels this action is in the best interest of the subject.

When a subject withdraws from the study, all of the necessary safety and tolerability assessments as described for Visit 9 should be obtained. Subjects experiencing adverse reactions should be followed until the reaction has resolved or is clearly determined to be due to a subject's stable or chronic condition. Appropriate supportive and/or definitive therapy will be administered as required.

Subjects will not be replaced.

The reason(s) for a subject's withdrawal from the study and their final assessments are to be recorded on the appropriate electronic case report form (eCRF) page.

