The week during which the day of the last dose occurs will be considered the last valid week during the 26-week treatment period, assuming it contains at least 4 valid daily IVRS diary days. Otherwise, the last valid week will be the preceding week. The last valid week during the treatment period will be used as the endpoint week for weekly efficacy summaries. If the last valid week is before week 12, the week 12 endpoint and week 26 endpoint will use this week. If the last valid week is after week 12, the week 12 endpoint will use week 12 and week 26 endpoint will use the last valid week obtained after week 12.

Only data captured from the first dose until the last dose will be used to derive the weeks during the 26-week treatment period,

All data listings will contain a relative study day, regardless of whether the data was collected via IVRS diary or eCRF.

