### **3.7.1 Efficacy Analyses**

The primary objective of this study will be to demonstrate the superiority of tenapanor over placebo in the proportion of subjects who are weekly overall responders at 6 or more of the first 12 weeks of treatment.

The ITT analysis set will be used for the analysis of the primary, key secondary, secondary, and all sensitivity analyses. The PP analysis set will be used for the analysis of the primary, key secondary, and secondary variables as a separate sensitivity analysis. All efficacy analyses will be carried out based on observed cases (OC) with imputation as described previously in [Section 3.3](#).

All efficacy variables involving responder rates or proportions will be analyzed using a Cochran-Mantel-Haenszel (CMH) test with pooled investigator site as a stratification (adjustment) variable. These analyses include subject based variables and variables summarized weekly. Summary statistics will include the pairwise risk difference with placebo along with the asymptotic 95% confidence interval (CI). The adjusted relative risk (adjusted for pooled investigator site) will be based on the ratio of responder rates for tenapanor 50 mg BID versus placebo. The 95% CI versus placebo will also be presented for the adjusted relative risk.

All change from baseline or percent change from baseline continuous efficacy variables derived from the daily IVRS questions (i.e., average weekly CSBMs, SBMs, stool consistency, straining score, abdominal symptoms of pain, discomfort, bloating, fullness, and cramping), as well as the weekly IBS severity, constipation severity, and IBS QOL will be analyzed using an analysis of covariance (ANCOVA) model with terms for pooled investigator site, treatment, and baseline as the covariate. These analyses include variables summarized weekly or on a visit basis.

Actual values for degree of relief of IBS symptoms and treatment satisfaction will be analyzed using an analysis of variance (ANOVA) model with terms for pooled investigator site and treatment.

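### The endpoint-week (LOCF) value for stool frequency and consistency can carry a severe-diarrhea week forward as benefit; make it descriptive and add an analysis that gives such withdrawals no credit

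*SAP*

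**What the plan says.** - **Endpoint week.** SAP 3.3 (and protocol 10.4) defines the endpoint as the last valid week, once within the first 12 weeks and once within the full 26: "This amounts to creating an endpoint last observation carried forward". Under SAP 3.5, a last valid week before Week 12 serves as both endpoints.
- **Which weeks qualify.** "A valid week will require at least 4 non-missing diary days" (SAP 3.3). "Only data captured from the first dose until the last dose will be used to derive the weeks" (SAP 3.5). If the week of the last dose is not valid, the preceding week is used.
- **Scoring.** Under SAP 2.3.1, the weekly CSBM and SBM figures are the sum divided by days reported, times 7. Stools within 24 hours after rescue medication are excluded; loose or watery stools are not.
- **Withdrawal.** Protocol 5.7 discontinues a subject from the study when "A subject experiences severe diarrhea defined by a Bristol Stool Form Score" of 6 or more, with at least 7 stools a day, on 2 consecutive days. Entry (protocol 5.4) required at most 5 SBMs a week and a mean BSFS of at most 3.
- **Week-by-week results.** "Change from baseline for each week of the 26-week treatment period will be summarized using the observed data" (SAP 2.3.1). The model is an "analysis of covariance (ANCOVA) model with terms for pooled investigator site, treatment, and baseline as the covariate" (SAP 3.7.1). No repeated-measures model is planned.
- **Status.** SAP 3.6 treats all secondary p-values as descriptive. The primary and key secondary variables are responder rates in which missing weeks count as non-response.

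**The concern.** Read together, these rules let the days that end a subject's participation supply the value that represents that subject at Weeks 12 and 26. Fourteen or more stools in two days, in someone who entered with 5 or fewer SBMs a week, score as a very large improvement. The times-7 standardization magnifies this when the final week is short. Protocol section 2 says the drug increases fluid in the gut, so such withdrawals are plausibly more frequent on tenapanor, and the error would then favour it.

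The responder endpoints take the opposite line: after discontinuation a week is a non-response. The one missing-data sensitivity analysis, counting missing weeks as response, covers responder rates only. The continuous outcomes have no equivalent, and SAP 3.7.1 plans no check of ANCOVA assumptions that might flag such extreme values.

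At stake are the reported continuous effect sizes and their confidence intervals, not the confirmatory tests.

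**Working it through.** **The plan's own figures.** The documents give none for the continuous outcomes. The stated power for the primary responder rate at 300 per arm reproduces: two-sided Fisher exact power is 96.1% at 45% vs 30% (stated 95%) and 80.8% at 45% vs 33.4% (stated 80%). Nothing below changes it.

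**What a withdrawal week scores.** Inputs from the documents: 2 days at 7 stools, at least 4 diary days, times-7 scaling. With *d* diary days in the week and other days at the baseline rate *b*/7:

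score = [14 + (*d* - 2) x *b*/7] / *d* x 7

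- *b* = 5: 27.0 with 4 diary days (change +22.0); 17.6 with 7 days (+12.6).
- *b* = 2: 25.5 with 4 days (+23.5); 15.4 with 7 days (+13.4).

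For consistency, take the 14 stools at BSFS 6. A 7-day week with no other stools, those five days scored 0, averages 84/19 = 4.4. A 4-day week with one BSFS 3 stool on each other day averages 90/16 = 5.6. Against a baseline of 3 these are changes of +1.4 to +2.6.

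**How often it counts, and the average excess.** Assumptions: background 5.5 SBMs a week (baseline 3 plus an average gain of 2.5), 7 stools on each diarrhea day, complete diaries, last dose on the second diarrhea day, that day equally likely to be any day of the study week, and a valid preceding week. The background is 5.5/7 = 0.786 a day, so each diarrhea day adds 7 - 0.786 = 6.214 stools.

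| Study-week day of last dose | Week used | Score | Excess over 5.5 |
|---|---|---|---|
| 1 | preceding week, one diarrhea day | 11.71 | 6.21 |
| 2 | preceding week, none | 5.50 | 0 |
| 3 | preceding week, none | 5.50 | 0 |
| 4 | final week, 4 days | 27.25 | 21.75 |
| 5 | final week, 5 days | 22.90 | 17.40 |
| 6 | final week, 6 days | 20.00 | 14.50 |
| 7 | final week, 7 days | 17.93 | 12.43 |

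For days 4 to 7 the excess is 2 x 6.214 x 7/*d* = 87/*d*. Both diarrhea days count in 4/7 of cases, one in 1/7 and none in 2/7. The mean excess is 72.29/7 = 10.3 stools a week.

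**Effect on the arm mean.** Inflation = fraction withdrawn x 10.3:

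- 1%: 0.10 per week
- 4%: 0.41 per week

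The treatment contrast moves by the difference between arms. With an assumed 0.5% on placebo, subtract 0.005 x 10.3 = 0.05, leaving about 0.05-0.36.

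**Would a repeated-measures model remove it?** A simulation used 200 trials per setting, 300 per arm, 12 weeks, a true difference of 1.0, SD about 2.5, 10% other dropout and 0.5% diarrhea withdrawal on placebo, all assumed. The diarrhea week was always the last observed week, with a change of +12.6 to +23. It therefore ignores the fallback rule and overstates the LOCF effect. Week 12 estimates:

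| Diarrhea withdrawal, tenapanor | LOCF | Repeated measures | Observed case | Those subjects at zero change |
|---|---|---|---|---|
| 1% | 1.04-1.13 | 1.00-1.06 | 0.98-1.01 | 0.96-0.99 |
| 3% | 1.24-1.50 | 1.08-1.20 | 0.98 | 0.92 |
| 5% | 1.49-1.96 | 1.21-1.39 | 0.99-1.01 | 0.89-0.92 |

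The model removes about half to two thirds of the LOCF inflation. The observed-case column is close to 1.0 because withdrawal was simulated independently of the subject's underlying weekly values; that is an assumption, not evidence that the late weeks are free of selection.

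**The case against.** The case against is substantial.

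- **Consequence is limited.** These outcomes lie outside the sequential test. In every confirmatory analysis, weeks lost to withdrawal count against the drug. This stands.
- **The tables do not hide withdrawals.** Reasons for early withdrawal and TEAEs leading to discontinuation are tabulated by arm (SAP 3.6.1, 3.8.1), and weekly results and figures accompany the endpoint. This stands, but none of it corrects the endpoint contrast. The per-protocol repeat excludes these subjects by conditioning on completion, so it does not count the withdrawal as failure.
- **The SAP is open about its definition**, namely the last experience on drug. True, but a summary can be clearly defined and still misread as a Week 26 treatment effect.
- **A mixed model is a preference and may be worse here.** In the simulation it lay further from the truth than the observed-case analysis already planned. This stands against offering the model alone.

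Two stronger readings are tempting. SAP 3.7.1 says "All efficacy analyses will be carried out based on observed cases (OC) with imputation as described previously in" Section 3.3, and a reader might infer that the weekly ANCOVAs also carry values forward. They do not: SAP 2.3.1 bases weekly change on observed data, and only the endpoint week is carried. Their weakness is different. Withdrawn subjects drop out, so later weeks compare those still on drug, which is sound only if withdrawal is unrelated to outcome given the model terms.

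A reader might also treat every such withdrawal as a full 7-day week with 1-2 stools on the other days, giving 19-24 stools and an inflation of 0.14-0.74 at 1-4%. That omits the validity, fallback and scaling rules, and a background of 7-14 stools a week conflicts with the assumed average of 5.5.

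**Conclusion.** The concern holds for the endpoint-week analysis of average weekly SBMs, stool consistency and, where stools are rated complete, CSBMs. It does not hold for the weekly observed-case ANCOVA, and it is not automatic for every diarrhea withdrawal: under the timing assumption above, 2/7 of them would carry no diarrhea day at all.

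The size is about 0.10-0.41 SBMs per week on the tenapanor mean. That rests on an assumed withdrawal rate of 1-4%, an assumed background of 5.5 a week, 7 stools on each diarrhea day and complete diaries. The documents give no withdrawal rate and no SD, so this shows direction and range and is not a forecast. The primary endpoint, the key secondaries, the type I error control and the sample size are untouched. The change is worth making because it is cheap and these analyses supply the continuous effect sizes.

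**What to change.** In SAP 3.3 and 3.7.1:

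1. Label the LOCF endpoint week descriptive for continuous outcomes, without a treatment p-value, or drop it.
2. For the Week 12 and Week 26 contrasts, prespecify a repeated-measures model on all weekly values, with treatment, week, treatment-by-week, pooled site, baseline and baseline-by-week, and a stated fallback covariance.
3. Report beside it, with equal prominence, an analysis that gives no benefit to subjects withdrawn under protocol 5.7 or for an adverse event, using the baseline value or reference-based imputation. State that the model in step 2 does not by itself deal with these withdrawals, since it extrapolates from the diarrhea week.
4. Show the number of such withdrawals by arm next to the continuous results.

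The cost is SAP text and modest programming. Protocol section 10 lets statistical changes be made in the SAP without a protocol amendment. The main practical downside is that 26 weekly time points may need a structured covariance or 4-week averages for the model to converge.
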